3.5 Study Procedures

3.5.1 Screening

Patients eligible for enrollment will be screened for inclusion and exclusion criteria by one of the approved study investigators. This includes assessment and documentation of patient's past and current medical history, current admitting diagnosis, medications on admission, physical exam, and

laboratory tests. If the patient meets inclusion and exclusion criteria, signed written informed consent will be obtained. Pregnancy test will be obtained in women of childbearing age.

3.5.2 Randomization

Implementation and documentation of the following procedures:

Vital statistics

Laboratory tests obtained

Blood drawn for cystatin C, plasma renin activity, NT-proBNP, and copeptin A

Urine sample (for future analyses)

Fluid balance and urine output

Body weight

Study drug dispensed and initiation time recorded

Administer dyspnea survey (Likert Scale)

3.5.3 8 hours

Implementation and documentation of the following procedures:

Vital statistics

Laboratory tests obtained

Fluid balance and urine output

Recording of any patient or physician reported adverse events

3.5.4 24 hours

Implementation and documentation of the following procedures:

Vital statistics

Laboratory tests obtained

Blood drawn for cystatin C, plasma renin activity, NT-proBNP, and copeptin A

Urine sample (for future analyses)

Fluid balance and urine output

Body weight

Recording of any patient or physician reported adverse events

Study drug continued and/or adjustments to treatment regimen

Administer change in dyspnea survey (Likert Scale)

3.5.5 48 hours

Implementation and documentation of the following procedures:

Vital statistics

Laboratory tests obtained

Urine sample (for future analyses)

Fluid balance and urine output

Body weight

Recording of any patient or physician reported adverse events

Study drug continued and/or adjustments to treatment regimen

3.5.6 72 hours

Implementation and documentation of the following procedures:

Vital statistics

Laboratory tests obtained

Blood drawn for cystatin C, plasma renin activity, NT-proBNP, and copeptin A

Urine sample (for future analyses)
 Fluid balance and urine output
 Body weight
 Recording of any patient or physician reported adverse events
 Study drug continued and/or adjustments to treatment regimen

3.5.7 96 hours

Implementation and documentation of the following procedures:
 Vital statistics
 Laboratory tests obtained
 Blood drawn for cystatin C, plasma renin activity, NT-proBNP, and copeptin A
 Urine sample (for future analyses)
 Fluid balance and urine output
 Body weight
 Recording of any patient or physician reported adverse events
 Study drug continued and/or adjustments to treatment regimen
 Administer change in dyspnea survey (Likert Scale)

3.5.8 Discharge from hospital

Implementation and documentation of the following procedures:
 Vital statistics
 Laboratory tests obtained
 Fluid balance and urine output
 Body weight
 Recording of any patient or physician reported adverse events

3.6 Removal of Patient from Study

If at any time the primary treating physician or the principal investigators feel it would be unsafe for the patient to continue on the study protocol, the patient will be discontinued from any further study procedures. The patient will continue to be followed for non-investigational related endpoints (vital statistics, daily weights, fluid balance, standard laboratory tests, and disposition) until discharge from the hospital.

4. Study Laboratory Assessments

4.1 Data Points

	Randomization	8 hours	24 hours	48 hours	72 hours	96 hours	Discharge
Vital Statistics	X	X	X	X	X	X	X
UO (Fluid Balance)	X	X	X	X	X	X	X
Weight	X		X	X	X	X	X
Serum Chemistries	X	X	X	X	X	X	X
Cystatin C	X		X			X	
PRA	X		X			X	

Copeptin	X		X			X	
NT-proBNP	X		X			X	

4.2 Study Laboratory Assessments

Neurohormonal activation has been implicated as a pathophysiologic mediator of acute worsening renal function and diuretic resistance in HF when conventional diuretics are utilized. However, vasopressin receptor antagonists do not appear to increase plasma renin activity, which provides a potential mechanism to support the safety of these agents over conventional diuretics. Copeptin is a marker for vasopressin activation and has been shown to have prognostic value in HF patients. In addition, it may be a useful marker to identify patients who may exhibit a greater response to vasopressin receptor antagonists. Cystatin C has been shown to have prognostic importance in acute HF and is a more stable marker of glomerular filtration rate compared to serum creatinine. These additional laboratory assessments will be obtained to provide a more complete pathophysiologic model for the safety comparison between the two treatment groups.

4.2.1 Assessments of Investigational Laboratory Parameters

Blood samples will be obtained for analysis of cystatin C, plasma renin activity, and copeptin A at baseline, 24 hours and 96 hours. Urine samples will be collected and stored for potential future analysis of renal injury markers.

4.2.2 Performance of Investigational Laboratory Parameter Assays

The investigational laboratory assessments (cystatin C and plasma renin activity) will be outsourced to Quest Diagnostics. Copeptin A will be determined using a commercially available immunoassay (Brahms Copeptin Immunoassay, Thermofisher Scientific, Middleton, VA).

5. Evaluation of Adverse Events

5.1 Definitions

Acute worsening of kidney function will be defined as an increase in Scr of 0.3 mg/dL or 25% above baseline (Scr at time of randomization).

Electrolyte abnormalities will be defined as an occurrence of a laboratory value beyond the upper or lower limit of normal as defined by the institution's laboratory standards (hypokalemia $K^+ < 3.5$ mEq/L, hypomagnesemia $Mg^{2+} < 1.7$ mEq/L, hypernatremia $Na^+ > 145$ mEq/L)

Serum sodium overcorrection will be defined as the occurrence of an increase in serum $Na^+ > 8$ mEq/L in 8 hours or > 12 mEq/L in 24 hours. For each event, any new neurologic sequelae (dysarthria, mutism, dysphagia, lethargy, affective changes, spastic quadriparesis, seizures, coma and death) of overcorrection will also be recorded, otherwise the subject will be noted to be asymptomatic.

Hypotension will be defined as a systolic blood pressure reading < 80 mmHg (confirmed by immediate repeat assessment) or a systolic blood pressure < 90 mmHg with symptoms.

In-hospital mortality will be defined as any study subject death during the hospitalization regardless of cause.

Safety Information will be collected in accordance with the current Code of Federal Regulations.

Safety information is defined as “Any information from any source containing information” such as:

- Adverse event or suspicion thereof
- Lack of efficacy
- Overdose, abuse, misuse (even without resulting adverse reaction)
- Medication error
- Exposure during pregnancy or lactation (including uneventful) and reports where the embryo or fetus may have been exposed to medicinal products (either through maternal exposure or transmission of a medicinal product via semen following paternal exposure)
- Counterfeit product
- Transfer of infectious disease by the medicinal product concerned
- Product complaint report which includes medically important information
- Pediatric use
- Occupational exposure
- Off-label use

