3.4.2 Study Drugs

Study drugs (and scheduled in-patient medications) will be administered in an open-label fashion.

Patients randomized to tolvaptan will receive the study medication orally once daily. Tolvaptan tablets will be administered at 24 hour intervals, scheduled based on when the initial dose is received.

Patients randomized to furosemide will receive the medication as a continuous infusion. The loop diuretic furosemide will be prepared as per standard procedures of the hospital pharmacy for administration via continuous intravenous infusion.

After the initial 24 hour monotherapy period, escalation of the treatment regimen for either study arm will be either based on a minimum urine output < 100 mL/h or otherwise at the discretion of the primary treating physician to achieve clinical goals (e.g. relief of dyspnea, improvement in peripheral edema, resolution of jugular venous distention, improvement in pulmonary congestion based on chest radiograph, etc.). Patients randomized to furosemide will not be eligible to receive tolvaptan as a mode to treatment escalation. Tolvaptan dose will not be increased if serum sodium rises > 8 mEq/8 hours or >12 mEq/24h.

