5.2 Reporting

Study subjects will be continuously monitored during the trial for the development of all serious and non-serious adverse events which were not present at the time of randomization in accordance with the current Code of Federal Regulations. This information will be obtained through examination of the patient, laboratory work-up, and discussion with the patient and/or nursing staff. All adverse events will be recorded and assessed for severity. Serious adverse events will be reported within 24 hours to Otsuka ([contact]), and the Food and Drug Administration AERS via the Medwatch website (Form 3500).

Otsuka will be notified of any adverse events or other safety information arising out of or relating to your study in accordance with the following timeline:

(a) Twenty-four (24) hours from Date of First Receipt for Serious AE's. (defined below);

A serious adverse event includes any event that results in any of the following outcomes: death, is life-threatening (opinion of the investigator that the subject was at immediate risk of death), persistent or significant disability/incapacity, requires in-patient hospitalization or prolongs hospitalization, congenital anomaly/birth defect, other medically significant events that, based upon appropriate medical judgment, may jeopardize the subject and may require medical or surgical intervention to prevent one of the outcomes listed above; or

(b) Three (3) working days for pregnancy cases; or

(c) End of study for non-serious adverse events or during the study upon Otsuka's request.

(d) At least two (2) weeks prior to submission of an aggregate safety report.

A line-by-line listing of all serious adverse events will be sent once fifty percent (50%) enrollment is reached and at the end-of-study in order for Otsuka Safety & Pharmacovigilance to perform a reconciliation.

The estimated start date for this study is August 15th, 2013. Data collection will be considered complete once the final study subject has been discharged from the hospital. This event is estimated to occur January 15th, 2015. A study report will be finalized within one year of the end of data collection.

6. Statistical Analysis

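### Electrolyte and kidney events can be met by one value from any draw, so if testing frequency differs between the open-label arms, the arm tested more could show more of these secondary events with no true difference

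*Combined protocol and SAP*

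**What the plan says.** Section 5.1 defines the laboratory safety events. For electrolytes: "Electrolyte abnormalities will be defined as an occurrence of a laboratory value beyond the upper or lower limit of normal". For the kidney: "Acute worsening of kidney function will be defined as an increase in Scr of 0.3 mg/dL or 25% above baseline". Neither definition asks for a confirming value, sets a time window, or says which draws count. Hypotension is handled differently: "Hypotension will be defined as a systolic blood pressure reading < 80 mmHg (confirmed by immediate repeat assessment", or a pressure below 90 mmHg accompanied by symptoms.

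The tables in sections 3.1.2 and 4.1 give one laboratory schedule for both arms: after randomization, chemistries at 8, 24, 48, 72 and 96 hours and at discharge. Section 5.2 draws adverse-event information from a wider base: "This information will be obtained through examination of the patient, laboratory work-up, and discussion with the patient and/or nursing staff".

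Section 3.4.2 states: "Study drugs (and scheduled in-patient medications) will be administered in an open-label fashion". It also sets a limit that applies to one arm only: "Tolvaptan dose will not be increased if serum sodium rises > 8 mEq/8 hours or >12 mEq/24h". Section 6.2 compares categorical endpoints by chi-square or Fisher's exact test and makes no allowance for the number of tests per patient. The primary safety endpoint in section 3.2.2 is mean creatinine change at 24 hours; electrolyte abnormalities and worsening kidney function are secondary.

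**The concern.** When one abnormal value is enough, a patient's chance of being counted rises with the number of values looked at. That does no harm to the comparison if both arms are sampled equally. Here clinicians order tests knowing the treatment, and an unscheduled panel can create an event.

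There are plausible reasons for extra draws in either arm. On tolvaptan, the dose limit refers to sodium rise over 8 hours or 24 hours. Escalation opens after 24 hours, and from then to 96 hours the scheduled draws are 24 hours apart, so a current 8-hour rise cannot be read from them. A clinician who wants to apply that part of the rule after 24 hours might order more sodium values. If these are sent as chemistry panels, they also return potassium and creatinine. On furosemide, a continuous infusion might prompt extra potassium or magnesium checks.

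At stake are the secondary counts that support the renal and electrolyte parts of Objective 2 and the hypothesis of fewer adverse events. If draws differ by arm, those counts would partly reflect testing frequency, and event counts alone could not separate the two.

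**Working it through.** **No stated figure to reproduce.** The plan gives no event rate, draw frequency or power for these endpoints. What follows is an illustration.

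**Inputs from the plan**
- Scheduled post-randomization chemistry draws: 6 (sections 3.1.2 and 4.1: 8, 24, 48, 72, 96 h and discharge), for a patient who stays past 96 h.
- Sample size: 34 to 46 in total under the August 2017 amendment (section 6.1), so 17 to 23 per arm.
- Test: Fisher's exact (section 6.2), two-sided 5%.

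**Assumptions, not in the plan**
- Probability p that a draw is abnormal, equal in both arms: 3%, 5% or 10%.
- Draws in the more-tested arm: 8 or 12, against 6.
- Within-patient correlation ρ on a latent normal scale: 0, 0.5 or 0.8.

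**Formulas.** For independent draws, P(at least one abnormal value) = 1 − (1 − p)^k. With p = 0.05:
- k = 6: 1 − 0.95^6 = 1 − 0.735 = 26%
- k = 8: 1 − 0.95^8 = 1 − 0.663 = 34%
- k = 12: 1 − 0.95^12 = 1 − 0.540 = 46%

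For correlated draws, each patient has a shared normal effect u, and P = 1 − ∫ φ(u) [1 − Φ((z_p − √ρ·u)/√(1 − ρ))]^k du, where z_p is the p-quantile of the standard normal. The chance of a false p ≤ 0.05 is the sum, over all pairs of binomial counts, of the probability of those pairs that Fisher's test rejects.

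**Results, p = 0.05, 23 per arm, no true difference**

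| Draws | ρ | Patients with an event | False significance |
|---|---|---|---|
| 6 v 6 | 0 | 26% v 26% | under 3% |
| 6 v 8 | 0 | 26% v 34% | 4.5% |
| 6 v 12 | 0 | 26% v 46% | 19% |
| 6 v 12 | 0.5 | 19% v 27% | 6% |
| 6 v 12 | 0.8 | 13% v 16% | 3% |

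**Range over p = 3% to 10%, 23 per arm**
- 6 v 12, independent: 13% to 30% falsely significant.
- 6 v 12, ρ = 0.5: 5% to 7%.
- 6 v 12, ρ = 0.8: 2% to 4%.
- 6 v 8, independent: 4% to 6%.

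At 17 per arm, 6 v 12 independent draws with p = 0.05 give 13%.

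**Reading.** With equal draws there is no bias. With unequal draws the two proportions differ in every row, even where the test rarely rejects. The large rejection rates need both a doubling of draws and little correlation between them.

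**The case against.** The strongest reply is that unequal testing is nowhere documented. Both arms share one schedule, no section orders extra draws in either, and the tolvaptan rule only bars a dose increase. It could be applied from the scheduled values at baseline, 8 and 24 hours. The overcorrection definition in section 5.1 ("Serum sodium overcorrection will be defined as the occurrence of an increase in serum" and so on) applies to both arms. Extra tests on furosemide could offset extra tests on tolvaptan. All of this stands: a reader might infer that one arm will be tested more, or that tolvaptan will look worse, and the documents support neither.

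A reader might also extend the point to hypotension. The definition does not allow that, since a reading below 80 mmHg needs an immediate repeat and one below 90 mmHg needs symptoms. More frequent checks could still find more episodes, but one isolated reading is not enough. Nor is the whole renal comparison exposed: creatinine change at 24 hours and GFR change are measured at set times.

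The objection to the size is also fair. Repeated potassium or creatinine values in one patient are unlikely to be independent, and a doubling of draws is a large contrast. Relaxing either assumption brings false significance close to or below 5%.

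Finally, restricting a safety count to scheduled values can hide true events. That argues for keeping the all-values count in view, but leaves the case for a like-for-like comparison intact.

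What survives is that the definitions leave the set of eligible values open, in a trial where the people ordering tests know the arm.

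**Conclusion.** The point holds for two secondary safety endpoints, electrolyte abnormality and acute worsening of kidney function, and as a possibility: testing frequency could differ by arm, and if so the more-tested arm could show more events with no true difference. Direction and size are unknown.

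On the stated assumptions the distortion runs from modest (13% versus 16% at correlation 0.8) to substantial (26% versus 46% with independent draws). The 19% false-significance figure, and the 30% at 10% per draw, are upper-end illustrations and should not be read as the expected error rate. No decision or stopping rule in the plan depends on these counts. The change is still worth making before analysis, because it is cheap and the scheduled values are already planned.

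**What to change.** In sections 5.1 and 6.2, for electrolyte abnormality and worsening kidney function only:

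- Base the between-arm comparison on the protocol-scheduled draws at 8, 24, 48, 72 and 96 hours, and state whether the discharge draw counts.
- Report the count from all values alongside it.
- Keep every event found on an unscheduled value in the adverse-event listing.
- Report the number of draws per patient by arm, scheduled and unscheduled. This also shows where early discharge has left some patients with fewer scheduled draws, which the restriction does not remove.

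Leave the hypotension comparison on all confirmed or symptomatic episodes. Monitoring and dosing need no change on account of this point.

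The cost is a few sentences and a flag on the case report form separating scheduled from unscheduled values. The downside is small: some true laboratory events between scheduled draws will appear only in the all-values count and the listing.

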5.2 Reporting

Study subjects will be continuously monitored during the trial for the development of all serious and non-serious adverse events which were not present at the time of randomization in accordance with the current Code of Federal Regulations. This information will be obtained through examination of the patient, laboratory work-up, and discussion with the patient and/or nursing staff. All adverse events will be recorded and assessed for severity. Serious adverse events will be reported within 24 hours to Otsuka ([contact]), and the Food and Drug Administration AERS via the Medwatch website (Form 3500).

Otsuka will be notified of any adverse events or other safety information arising out of or relating to your study in accordance with the following timeline:

(a) Twenty-four (24) hours from Date of First Receipt for Serious AE's. (defined below);

A serious adverse event includes any event that results in any of the following outcomes: death, is life-threatening (opinion of the investigator that the subject was at immediate risk of death), persistent or significant disability/incapacity, requires in-patient hospitalization or prolongs hospitalization, congenital anomaly/birth defect, other medically significant events that, based upon appropriate medical judgment, may jeopardize the subject and may require medical or surgical intervention to prevent one of the outcomes listed above; or

(b) Three (3) working days for pregnancy cases; or

(c) End of study for non-serious adverse events or during the study upon Otsuka's request.

(d) At least two (2) weeks prior to submission of an aggregate safety report.

A line-by-line listing of all serious adverse events will be sent once fifty percent (50%) enrollment is reached and at the end-of-study in order for Otsuka Safety & Pharmacovigilance to perform a reconciliation.

The estimated start date for this study is August 15th, 2013. Data collection will be considered complete once the final study subject has been discharged from the hospital. This event is estimated to occur January 15th, 2015. A study report will be finalized within one year of the end of data collection.

6. Statistical Analysis

6.1 Sample Size Calculation and Power Analysis

A total of 50 patients (25 in each group) would provide 93% power to detect a difference of 50% in urine output at 24 hours between treatments, $\alpha=0.05$. The power was calculated based on the magnitude of difference in urine output seen in the ACTIV-CHF²⁰ (24 hour mean urine output for tolvaptan was approximately $4100\pm 2100\text{mL}$ vs $2300\pm 1100\text{mL}$ compared to placebo when added to standard therapy) and in the Udelson et al²³ study (24 hour mean increase in urine output with tolvaptan monotherapy $2600\pm 1500\text{mL}$ vs $900\pm 850\text{mL}$ with furosemide). Based on our previous data demonstrating poor response to loop diuretics in the hyponatremia acute HF population, we believe a 50% difference (standard deviation of 25%) is a reasonable and conservative estimate of what the difference will likely be.

Amendment August 9, 2017:

Due to slow enrollment, we anticipate not achieving our desired sample size of 50 subjects. Our revised power calculation reveals that if we achieve a mean difference with the same magnitude standard deviation between groups (e.g. mean difference is $1000\pm 1000\text{mL}$), our power will be between 80-90% with a sample size between 34-46 subjects. Based on current rate of enrollment, it is likely that we will achieve a sample of at least 34 subjects, which should allow the results to be meaningful despite early termination of enrollment.

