
Primary Endpoints
	
Primary efficacy endpoint: Mean urine output at 24 hours post randomization Primary safety endpoint: Mean change in serum creatinine at 24 hours post randomization

Secondary Endpoints
	
Efficacy: Urine output at 8, 48, 96 hours post-randomization, total at discharge Mean hourly urine output at 24 hours Serum sodium change at 8, 24, 48, 96 hours, and at discharge Weight change at 24, 48, 96 hours, and at discharge Cumulative furosemide dose at 48, 96 hours, and at discharge Cumulative use of metolazone at 48, 96 hours, and at discharge Self-rated change in dyspnea (Likert Scale) at 24 and 96 hours Safety: GFR change at 24, 48, 96 hours, and at discharge (estimated from Scr) Acute worsening of kidney function (increase in Scr 0.3 mg/dL or 25% above baseline) Electrolyte abnormalities (hypokalemia, hypomagnesemia, hyper/hyponatremia) Hypotension Changes in plasma renin activity, copeptin, cystatin C concentrations, NT-proBNP In-hospital mortality Hospital length of stay (ICU and total)

Statistical Plan
	
A total of 50 patients (25 in each group) would provide 93% power to detect a difference of 50% in urine output at 24 hours between treatments, alpha=0.05. The power was calculated based on the magnitude of difference in urine output seen in the ACTIV-CHF (24 hour mean urine output for tolvaptan was approximately 4100±2100mL vs 2300±1100mL compared to placebo when added to standard therapy) and in the Udelson et al study (24 hour mean increase in urine output with tolvaptan monotherapy 2600±1500mL vs 900±850mL with furosemide). Based on our previous data demonstrating poor response to loop diuretics in the hyponatremia acute HF population, we believe

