	
a 50% difference (standard deviation of 25%) is a reasonable and conservative estimate of what the difference will likely be.
 
Descriptive statistics will be computed for each treatment group. For all comparative analyses between the two treatment groups, independent samples t-test and Chi-Square test (or Fisher’s exact test) will be performed for continuous variables or categorical variables, respectively. If either the normality or equal-variance assumptions underlying the traditional t-tests are violated, a non-parametric test will be used.
 
Amendment August 9, 2017: Due to slow enrollment, we anticipate not achieving our desired sample size of 50 subjects. Our revised power calculation reveals that if we achieve a mean difference with the same magnitude standard deviation between groups (e.g. mean difference is 1000±1000mL), our power will be between 80-90% with a sample size between 34-46 subjects. Based on current rate of enrollment, it is likely that we will achieve a sample of at least 34 subjects, which should allow the results to be meaningful despite early termination of enrollment.

Study Duration	18 months

Table of Contents

	Page
List of Abbreviations	6
1. Introduction	7
2. Study Rationale and Objectives	9
3. Study Design	

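### The 25% planning SD matches neither the cited trials nor the stated 93% power, and the amended 80–90% power holds only if the difference equals its SD

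*Combined protocol and SAP*

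**What the plan says.** The sample size paragraph appears in section 6.1 and again in the Statistical Plan row of the synopsis. It makes four statements.

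- The target: "A total of 50 patients (25 in each group) would provide 93% power to detect a difference of 50% in urine output at 24 hours", at alpha 0.05. Sidedness is not stated.
- The evidence from ACTIV-CHF: "24 hour mean urine output for tolvaptan was approximately 4100±2100mL vs 2300±1100mL compared to placebo when added to standard therapy".
- The evidence from the monotherapy study: "24 hour mean increase in urine output with tolvaptan monotherapy 2600±1500mL vs 900±850mL with furosemide".
- The planning values: "a 50% difference (standard deviation of 25%) is a reasonable and conservative estimate of what the difference will likely be". The base of the 25% is not stated. The reason given is the investigators' own earlier data on poor response to loop diuretics.

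The amendment of August 9, 2017 adds a condition, that the mean difference is of the same size as its SD. Its example is "mean difference is 1000±1000mL", and it concludes that "our power will be between 80-90% with a sample size between 34-46 subjects". From this it infers that at least 34 subjects should still give meaningful results although enrolment stops early. No source is given for the 1000 mL. Section 6.2 names the independent samples t-test, with a non-parametric test if its assumptions fail.

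**The concern.** The paragraph cites two trials with widely spread 24-hour urine output and then plans with a much smaller spread. The only argument offered, poor response to loop diuretics, bears on the size of the difference, not on its variability. The amendment reduces the difference from the cited 1700–1800 mL to an example of 1000 mL and reduces the SD along with it. Reducing the difference is cautious. Reducing the SD works in the opposite direction.

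Urine output at 24 hours is the primary efficacy endpoint, and the amended power is the stated ground for accepting fewer than 50 patients. If the SD is nearer the cited values, a true 1000 mL difference could be missed quite often, and a reader relying on 80–90% power could give a non-significant result more weight than it deserves.

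**Working it through.** **Method.** Two-sample t-test, two-sided alpha 0.05 (assumed), equal arms, no dropout. With n per arm and d = difference/SD, power comes from the noncentral t distribution with 2n − 2 degrees of freedom and noncentrality d·√(n/2). Pooled SD = √((s₁² + s₂²)/2).

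**1. The 93% figure.** With the printed inputs, d = 50/25 = 2, and 25 per arm gives power above 99.9%; about 7 per arm would already give 93%. A one-sided test, alpha 0.01, a 25% CV in each arm and a log scale all leave power above 99.9%. At d = 1, 25 per arm gives 93.4%. Solving for exactly 93% gives d = 0.992, an SD of 50/0.992 = 50.4%. So the 93% reflects an SD of about 50%.

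**2. The amended figure.** At d = 1, 17 per arm gives 80.7% and 23 per arm gives 91.2%. The stated 80–90% is reproduced.

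**3. The cited variability.**

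| Trial | Arm | Mean, mL | SD, mL | SD/mean |
|---|---|---|---|---|
| ACTIV-CHF | tolvaptan | 4100 | 2100 | 51% |
| ACTIV-CHF | placebo | 2300 | 1100 | 48% |
| Monotherapy study (increase) | tolvaptan | 2600 | 1500 | 58% |
| Monotherapy study (increase) | furosemide | 900 | 850 | 94% |

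- ACTIV-CHF: pooled SD = √((2100² + 1100²)/2) = 1676 mL; d = 1800/1676 = 1.07.
- Monotherapy study: pooled SD = √((1500² + 850²)/2) = 1219 mL; d = 1700/1219 = 1.39.

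The printed 25% is below all four relative SDs. The 1000 mL is below both pooled SDs and three of the four arm SDs, but above the 850 mL of the furosemide arm.

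**4. Power for a 1000 mL difference.** The first and third rows below the amendment's own SD keep the cited absolute SDs. The other two keep each arm's SD/mean ratio and set the tolvaptan mean 1000 mL above the cited control mean:

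- Monotherapy study, 1900 v 900 mL: tolvaptan SD = 1900 × 1500/2600 = 1096; pooled √((1096² + 850²)/2) = 981 mL.
- ACTIV-CHF, 3300 v 2300 mL: tolvaptan SD = 3300 × 2100/4100 = 1690; pooled √((1690² + 1100²)/2) = 1426 mL.

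| SD, mL | Basis | d | N=34 | N=46 |
|---|---|---|---|---|
| 1000 | amendment's example | 1.00 | 81% | 91% |
| 1219 | monotherapy study, SDs as cited | 0.82 | 64% | 78% |
| 981 | monotherapy study, ratios held | 1.02 | 82% | 92% |
| 1676 | ACTIV-CHF, SDs as cited | 0.60 | 39% | 51% |
| 1426 | ACTIV-CHF, ratios held | 0.70 | 51% | 64% |

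A Welch test simulated with the cited unequal SDs agrees: 38% and 50% for ACTIV-CHF, 64% and 77% for the monotherapy study.

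**5. Difference detectable with 80% power.** The required d is 0.991 at 17 per arm and 0.845 at 23 per arm. Over SDs of 1000 to 1676 mL this is 991 to 1661 mL at N=34 and 845 to 1416 mL at N=46.

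**6. If the full cited effects occur.** At N=34, power is 86% (1800 mL, SD 1676) and 98% (1700 mL, SD 1219).

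**The case against.** The strongest defence is that the amendment is correct as written. It is a conditional statement about d = 1, the 1000 mL values are only an example, and d = 1 is smaller than either cited standardised effect (1.07 and 1.39). A 50% difference is likewise below the cited relative differences of 1800/2300 = 78% and 1700/900 = 189%, so *conservative* is fair for the difference itself. All of this stands. A reader might infer that the amended power is an arithmetic error, or that the study is underpowered for the effects it cites. The documents support neither.

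A reader might also infer that 1000 mL contradicts every cited SD and should be struck out. That goes too far. The furosemide arm, the only cited arm on this trial's comparator drug, has an SD of 850 mL. In both trials the arm with the higher mean has the larger SD, so a smaller difference may well bring a smaller SD. Holding the monotherapy study's ratios gives 981 mL, which supports the example.

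Neither trial transfers cleanly. By the protocol's own account, the monotherapy study enrolled stable patients on fixed oral doses; the figures cited from it are increases in urine output, whereas the endpoint is output. ACTIV-CHF tested tolvaptan added to standard therapy. The pooled SDs are therefore reference points, not established values for this population.

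What the defence does not remove is the printed 25%, which agrees with neither the cited data nor the 93%. Nor does it supply a source for 1000 mL, and the conclusion about meaningful results is drawn without repeating the condition on which the power depends.

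**Conclusion.** The point holds in two parts. First, the 50% difference, 25% SD, 50 patients and 93% power are mutually inconsistent; an SD of about 50% restores consistency and is close to three of the four cited relative SDs (48%, 51%, 58%). Correcting it leaves the 50-patient target and its 93% unchanged. Second, the amended 80–90% is right at d = 1, but the 1000 mL example sits at the favourable end of what the cited data allow. For a 1000 mL difference, power could be as low as 39% at N=34 and 51% at N=46.

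The low end assumes that ACTIV-CHF's absolute SDs carry over unchanged to a smaller difference; holding its ratios instead gives 51% and 64%. All figures assume a two-sided test, equal arms and no dropout. The shortfall concerns the reduced difference used as the example, not the full cited effects.

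**What to change.** In section 6.1 and the Statistical Plan row of the synopsis:

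1. Replace the SD of 25% with the value that gives 93% (about 50%), and state the base of the percentage and the sidedness of the test.
2. Apply *conservative* to the size of the difference only.
3. Give a source for the 1000 mL SD if there is one, and restate the amended power as a range. Suggested text: For a 1000 mL difference and SDs of about 1000 to 1680 mL, power is 81% down to 39% with 34 subjects and 91% down to 51% with 46; at an SD of 1219 mL it is 64% and 78%. Power of 80% needs a true difference of about 990 to 1660 mL with 34 subjects, or 840 to 1420 mL with 46. The full effects of the cited trials would give 86% to 98% with 34.
4. Make the statement that results will be meaningful after early termination conditional on these figures.

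The cost is one reworded paragraph in two places and a less favourable stated power. Enrolment, design and analysis are unchanged.
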